Prior to any statistical tests, descriptive statistics, *including* histograms, box plots or scatter diagrams, will be used to assess distribution of variables and their inter-relationships, as well as to detect missing data and outliers for outliers that are deemed to be legitimate values, two types of analyses will be performed and the results compared and reported: the first analysis will include the outliers, and the second will exclude them. Transformations, such as logarithmic or square root transformations will be used for variables with skewed distributions, prior to their inclusion in any analyses that require normality or approximate normality. If normality cannot be achieved through transformations, then non-parametric techniques will be used. Bivariate analyses (e.g., chi-square tests, t tests) will be used to assess patterns of association of factors potentially associated with outcome measures. Appropriate correlational analyses will be performed for each of the independent variables as well as with the outcome variables to identify factors related to outcomes or that are likely to be confounders. Factors that will be considered as potential confounders are those observed to have moderate associations (using a liberal size for preliminary tests of association such as $\alpha=0.25$) with appointment adherence as well as with independent variables specified in the hypotheses. These variables will be controlled for in analyses for specific hypotheses, as appropriate.

Primary Analytic Strategy

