Our plan for the main analyses is to use the General Mixed Model (Ware, 1985), which is an analytic strategy that can be employed for the hypotheses under each specific aim. This model is suitable for analysis of unbalanced data, does not require the assumption of normality of the dependent variable (in fact it can be used when the response of interest is a binary variable or a count variable), can incorporate account for missing data in statistical models and is implemented in different analytical software packages such as the Proc MIXED in SAS. In addition to the longitudinal analysis, the model also permits cross-sectional analyses (comparing outcomes by condition), which we will perform at baseline, and at the post intervention follow-up. In addition, to the cross-sectional analyses comparing the main effect of treatment we will also examine main effects for race/ethnicity and treatment by race interactions. We have specified primary outcome variables for both the caregiver (e.g., CESD) and patient (e.g., HVLT-R). However, as the intervention targets a number of different areas related to patient and caregiver outcomes there are a number of secondary measures. When possible, we will examine and employ a multivariate approach. Using a set of measures that are included in our outcome battery, Schulz et al (2009) created a multivariate outcome and we will employ a similar approach. For the cognitive variables, composite measures will be created using principal axis factoring approaches or selecting measures that load most highly on derived factors representative of a particular domain (e.g., memory).

For each hypothesis, we will consider models that incorporate covariates and interactions in order to examine the effects of potential mediator and moderator variables on outcomes. For example, a potential mediator of caregiver outcomes is improvement in both cognitive and functional status of the patient, which will be incorporated in longitudinal models of change. Similarly, training dosage and adherence to homework assignments captured in real time on the tablet will be examined in relation to outcomes. We are aware that given the relatively modest sample size available for some of the analyses, careful consideration must be given to potential problems such as over parameterization; thus, only a limited number of covariates will be included in each model.

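### The sentence that decides which covariates are adjusted for screens factors against an undefined variable and the randomised condition; it states no prognostic criterion, and no adjustment set is named for the primary outcomes

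*Combined protocol and SAP*

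**What the plan says.** All of this is in section 7 (Data Management) of the combined protocol and SAP.

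Under Preliminary Analyses, correlations of candidate factors with the independent variables and the outcomes are planned "to identify factors related to outcomes or that are likely to be confounders". No threshold is attached to that step. The next sentence sets the criterion: "Factors that will be considered as potential confounders are those observed to have moderate associations", at a level such as 0.25, "with appointment adherence as well as with independent variables specified in the hypotheses". The consequence follows: "These variables will be controlled for in analyses for specific hypotheses, as appropriate".

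Under Primary Analytic Strategy, the main method is fixed: "Our plan for the main analyses is to use the General Mixed Model". A further comparison is added: "the model also permits cross-sectional analyses (comparing outcomes by condition), which we will perform at baseline, and at the post intervention follow-up". On covariates the plan says that "only a limited number of covariates will be included in each model". It names none for the primary outcomes, for which the CESD and the HVLT-R are given as examples. Race/ethnicity appears only as a main effect and in an interaction with treatment.

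**The concern.** Covariates in a randomised comparison are useful when they predict the outcome. The sentence that triggers adjustment here asks for something else.

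- **First screen.** Appointment adherence is not defined, is not an outcome in any hypothesis, and appears nowhere else in the available text. The nearest item is the exploratory plan that "training dosage and adherence to homework assignments captured in real time on the tablet will be examined in relation to outcomes".
- **Second screen.** Hypotheses 1.1, 1.2 and 2.1 (section 2) contrast only the assigned conditions. A test of a baseline factor against the independent variable is therefore a baseline imbalance test.
- **Link between them.** The wording can be read as requiring both associations or as accepting either.

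Two analysts following this text could fit different models to the same data, and the sponsor cannot say in advance what the treatment estimate is adjusted for. A strongly prognostic factor, such as the baseline score of the outcome, could be omitted because the arms happened to be balanced on it.

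**Working it through.** The plan gives no power, effect size or SD for the primary outcomes, so there is no stated figure to reproduce.

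**Inputs from the document:** screening level 0.25 (section 7); two randomised arms; 240 dyads (section 2) or 120 dyads (section 15). These two sizes conflict, so both are run.

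**Assumed:** 1:1 allocation; standardised effect d = 0.3; baseline-outcome correlation r = 0.5 or 0.7 with equal variances; correlation of the baseline score with adherence a = 0 or 0.2; the baseline score as the only screened factor.

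**Step 1: what appointment adherence could mean.**
- *The baseline visit*, which sections 5 and 18 call an appointment. Randomisation follows the baseline assessment (section 5), so every randomised dyad has kept it and there is nothing to correlate with.
- *Session attendance*. This arises after participants learn their condition, and care recipients may ask for fewer sessions (section 5).
- *Attendance at the 6- and 12-month assessments* (sections 5 and 11). This is also post-randomisation.
- *A slip for the outcome*. Tested in step 2.

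**Step 2: chance that the baseline score is selected.** Under randomisation it passes the test against arm with probability 0.25, whatever r is.
- Both required, a = 0: 0.25 × 0.25 = 0.0625.
- Both required, a = 0.2: the adherence screen is passed with probability 0.852 (120 dyads) or 0.976 (240 dyads), giving 0.25 × 0.852 = 0.213 and 0.25 × 0.976 = 0.244.
- Upper limit with both required: 0.25 × 1 = 0.25.
- Slip for the outcome, both required: the first screen is passed almost always, so again 0.25 (simulated 0.242-0.259).
- Either sufficient: 1 − 0.75² = 0.4375 for a = 0; for a = 0.2, 1 − 0.75 × 0.148 = 0.889 and 1 − 0.75 × 0.024 = 0.982.

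**Step 3: power of the post-intervention cross-sectional comparison.** Noncentral t, two-sided 0.05, noncentrality d√(n/2)/√(1 − r²) with n per arm, and r = 0 in the formula when unadjusted. At 240 dyads, 0.3 × √60 = 2.324; dividing by √0.75 gives 2.683 and by √0.51 gives 3.254. At 120 dyads, 0.3 × √30 = 1.643. The joint rule (both required) was simulated with 20,000 replicates over the four (r, a) pairs.

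| Dyads | Unadjusted | Joint rule | Baseline always included (r = 0.5 / 0.7) |
|---|---|---|---|
| 240 | 0.64 | 0.65-0.72 | 0.76 / 0.90 |
| 120 | 0.37 | 0.37-0.41 | 0.47 / 0.63 |

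Replacing adherence by the outcome, with both still required, gives 0.67-0.72 and 0.38-0.42. On the either/or reading power is 0.70-0.89 and 0.41-0.59. At 240 dyads and d = 0.5 the gain from adjustment is negligible (0.97 to 0.99-1.00).

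**Step 4: type I error.** Simulated null rejection is 0.026-0.047 with both required and 0.032-0.050 with either sufficient. There is no inflation; the test is at or below its nominal level.

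**Step 5: the main mixed model, 240 dyads, d = 0.3.**
- Baseline as a response constrained equal across arms: about 0.76-0.90 with no added covariate, so nothing is lost.
- Contrast of change: variance 2(1 − r). For r = 0.5 this is 1.0, noncentrality stays 2.324, and power is 0.64 against 0.76. For r = 0.7 it is 0.6, noncentrality is 2.324/√0.6 = 3.00, and power is 0.85 against 0.90.

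**The case against.** The strongest reply has five parts.

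- **The main analysis may already use baseline.** The longitudinal mixed model is primary and the cross-sectional comparison is additional. A reader might infer from step 3 that the main analysis loses the same power. The document does not support that: step 5 shows the loss runs from none upward, depending on a choice the plan does not state. This part stands and limits the size of the point.
- **The plan does look at prognosis.** Correlations with outcomes are planned, so it would be too strong to say that prognosis is ignored. That stands. But the step has no threshold and no stated link to adjustment, and the sentence that defines confounders does not use it.
- **Appointment adherence may have a sensible meaning.** Baseline predictors of missed follow-up can support the missing-data assumption of a likelihood-based model. That is possible, but the plan does not say it, and it would not justify the test against arm.
- **The rule is not mechanical.** The text speaks of potential confounders, offers 0.25 as an example, adds a qualifier on appropriateness and caps the number of covariates. The selection rates above describe the rule applied literally. This is fair, but the discretion makes the final model less predictable.
- **False positives.** A reader might infer that the rule inflates type I error. Applied automatically it does not. An analyst who reported the better of the unadjusted and baseline-adjusted results would reach about 0.07-0.08, but the plan nowhere proposes that.

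**Conclusion.** The point holds as a defect of specification and of method, and should be fixed. The adjustment criterion rests on an undefined variable and a test against the randomised arm, and no covariate set is named for the primary outcomes. With both associations required, a prognostic baseline factor is kept at most about 25% of the time, and correcting a possible slip for the outcome does not change that. These statements rest on the text, on randomisation and on the 0.25 level; they do not depend on which sample size applies.

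The power figures carry less weight. They depend on assumed d and r (and, for the joint rule, on a), and the large gap applies only to the additional cross-sectional comparison. Even there the rule does no worse than no adjustment; what is lost is the gain from always including the baseline score. For the main mixed model, loss of precision is possible but not shown.

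**What to change.** For the randomised comparisons in section 7, delete the 0.25 screen, the reference to appointment adherence, and any test against arm as a way to choose covariates. Then pre-specify one of two options for every primary model:

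1. adjust for the baseline value of that outcome; or
2. take the 6- and 12-month arm contrasts from a mixed model with baseline as a response constrained equal across arms.

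The second option also keeps dyads whose baseline measure is missing, which matters because virtual assessments may omit some measures (section 5). Site may be added as a fixed term if named in advance; it is optional, since no stratified randomisation is described. Confirm that the HVLT-R is collected at baseline, because the care recipient measures listed in section 5 do not name it.

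Keep factor screening, against the trial outcomes, only for the dosage, homework-adherence and mediator analyses, labelled exploratory.

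The cost is a few sentences and one or two degrees of freedom per model. Outcome comparisons at baseline are already planned, so apart from the HVLT-R check no new data should be needed.

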Appendix A:

CP Program Telephone Follow-Up Assessment

Measure	# of Items
Caregiver	
ADL/IADL Modified	11
Caregiving Medical Nursing Tasks	15
*Burden Interview	12
Positive Aspects of Caregiving	11
*CESD	11
Social Support	12
Use of Formal Care and Services	Only items: 1,2, 5-8
Quality of Life	1
Caregiver Preparedness	6
Caregiving Self-efficacy	9
Caregiver Self Health Rating	Only items: 1,2
Loneliness	20
CP/Nutrition Evaluation	21
*Cognitive Decline of CR Scale	Change stem as compared to the last six months and ask items: 1 -6
Care Recipient	
Quality of Life AD	
CESD	

Before asking the scale items on the Cognitive Decline of CR Scale (items 1 – 6) Please ask the CG the following question:

•
“Compared to six months ago has your partner’s (Care recipient) cognition:

Gotten Much Worse, (2) Gotten Slightly Worse, (3) Stayed the Same, (4) Gotten Slightly Better (5)
Gotten Much Better?

At the end of the Evaluation for CP ask the CG in the CP condition the following questions:

To what extent did your partner use the organizational tool?

(1) Very frequently (2) Frequently (3) Occasionally (4) Rarely (5) Never

How often did your partner do the computer exercises?

(1) Very frequently (2) Frequently (3) Occasionally (4) Rarely (5) Never

I found the organizational tool valuable?

(1) Strongly agree (2) Agree (3) Neither agree or disagree (4) Disagree (5) Strongly Disagree

The computer exercises were beneficial for my partner

(1) Strongly agree (2) Agree (3) Neither agree or disagree (4) Disagree (5) Strongly (2) Disagree

At the end of the Evaluation for CP ask the CG in the Nutrition condition the following questions:

How often did your partner do the computer exercises?

(2) Very frequently (2) Frequently (3) Occasionally (4) Rarely (5) Never

The computer exercises were beneficial for my partner

(3) Strongly agree (2) Agree (3) Neither agree or disagree (4) Disagree (5) Strongly Disagree
